**Emotion Discussion with Dyadic Neurofeedback Task.** This task will be completed in the scanner using simultaneous hyperscanning data collection. Prior to the fMRI, adolescents (without the parent present) will be asked to think of recent situations when they were feeling strong negative emotions, such as anger, sadness, and/or anxiety. They will be informed that they will be talking to their mother about each situation during the scan. The mother (without the daughter present) will be provided with task instructions and informed that while talking to her daughter she will be receiving neurofeedback from a region in her daughter's brain. The mother will be told that her goal is to decrease activation in that region by calming her daughter and decreasing the intensity of her daughter's emotional response. The emotion discussion task will consist of four types of trials, each lasting 40s: Rest trials, Count trials, Discussion trials, and Reflection trials. During the first Discussion trial, the adolescent will describe the emotional situation. This will be followed by a second Discussion trial during which the mother will respond to the adolescent while receiving neurofeedback from the adolescent's aIC. This will be followed by a Count trial during which participants will mentally count backward from 300 by a number specified on the screen (for example, by 6: 300, 294, 288...) in order to bring aIC activation back to baseline. This will be followed by a 40s Rest period. Following the Rest trial, the adolescent will be provided 40s to respond to her mother (no neurofeedback presented), and the mother will subsequently respond again to the adolescent while receiving neurofeedback from her daughter's aIC. This will again be followed by a Count and Rest trial. Finally, both the adolescent and her mother will be asked to mentally (i.e., silently) reflect on the discussion while receiving neurofeedback representing the synchrony between both participants' aIC activation. This will be followed by another 40s Count trial and 40s Rest trial, for a total runtime of 8 minutes. Participants will complete three runs of the emotion discussion task with dnf, followed by a fourth transfer run in order to determine if the effects of the training persist. During the transfer run, the task will be exactly the same except no neurofeedback will be presented.

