**ANALYSES:** Data will be analyzed in real-time with LIBR software. An automated script will generate an anatomically-defined spherical region-of-interest (5mm radius) centered at the aIC (locus: [38, 16, 4], MNI space). The dnf, updated every 2s and shown as a bar with moving height, will be measured as % signal change relative to baseline (obtained by averaging the fMRI signal for the preceding 40s rest block). To reduce bar fluctuations due to noise in the fMRI signal, bar height will be computed at every time point as the mean of the current and two preceding fMRI signal change values. All offline fMRI data preprocessing and analyses will be conducted as described elsewhere. General Linear Models (GLM) will be used to analyze individual subjects' data with predictors in the model. Regressors of non-interest will be included in all models to account for each run's signal mean, linear, quadratic, and cubic signal trends, as well as motion parameters. Regressors will also include the block stimulus conditions (daughter: Describe/Respond, Listen, Count, Rest, Reflect; mother: Respond [dnf], Listen, Count, Rest, Reflect) and five polynomial terms for modeling the baseline. The GLM  $\beta$  coefficients will be computed for each voxel and converted to % signal change for contrasts of interest (e.g., Listen versus Count, Listen versus Rest, Count versus Rest, Reflect versus Rest, and Reflect versus Count). Statistical contrast maps for exploratory whole-brain analyses will include corrections for multiple comparisons.

**Hypothesis 1A.** *Mothers will perceive that they are able to influence their daughters' aIC activation using the daughter's fMRI neurofeedback signal (e.g., dnf), based on rating scales presented at the end of each run (i.e., average rating of ability to move bar  $\geq 5/10$ ).* We will ask the mother to rate how effective she felt she was at changing her daughter's brain activity on a Likert scale from 0-10. For this analysis, we will simply take the mean of all parent participants' responses over all runs and determine if it is at least 5, providing evidence that mothers perceived they were able to effectively regulate their daughter's brain activity.

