**Hypothesis 1B.** *Mothers and daughters will be able to establish and maintain temporal synchronous aIC activation while reflecting on their interaction.* Correlations will be calculated between mothers' and daughters' aIC timecourses (Reflect vs Rest contrast).

**Hypothesis 2A.** *Mothers' own aIC activation while listening to their daughters will be positively correlated with that of their daughters' during the mothers' response.* The correlation between the mothers' and daughters' average beta weights for aIC activation during each participant's Listen trials will be calculated.

**Hypothesis 2B.** *Stronger temporal synchrony and coupling between mothers' and daughters' aIC activation during the reflection condition will be associated with more coded validation statements during the task and lower self-report ratings of negative emotions in both participants.* a) Coupling will be measured as the correlation between timecourses for aIC activation as described in Hypothesis 1B, transformed to z-scores (Fisher's r-to-z transformation). b) Participants will be asked to rate the intensity of various emotions they felt during the scan (0-10 Likert scale). Correlations will be calculated between the z-scores (a) and 1) the number of validating statements made by the mother across the scan and 2) ratings of negative emotions (b).

**Hypothesis 3A (Exploratory).** *Mothers' and daughters' neural activation of resting-state networks will be more temporally synchronous at the end of the hyperscanning session (following neurofeedback), as compared to their first resting-state fMRI scans in the hyperscanning session.* Similarity of resting-state networks will be evaluated as described in Lee et al. (2017). ICA will identify intrinsic resting-state networks at the group level. On the individual level, a matrix of correlation coefficients for all possible pairs of resting-state networks will be created and transformed to Fisher's z, then vectorized and correlated between each pair of mother-daughter dyads to determine the level of synchrony within the dyad. A paired t-test will be conducted to determine if there is a significant difference between resting-state synchrony at the beginning versus end of the scanning session.

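### Hypothesis 1B's mother-daughter correlation has no criterion and no unrelated-pair comparison, and a shared response to the Reflect block could make it positive without dyad-specific coupling

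*Combined protocol and SAP*

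**What the plan says.** All places are in the combined protocol and SAP.

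- **ANALYSES, Hypothesis 1B.** The whole analysis is: "Correlations will be calculated between mothers' and daughters' aIC timecourses (Reflect vs Rest contrast"). No null value, test, threshold, or rule for combining runs and dyads follows.
- **Other hypotheses.** For 1A the plan takes the mean rating over mothers and runs and will "determine if it is at least 5". For 3A and 3B it names paired t-tests.
- **Emotion Discussion with Dyadic Neurofeedback Task.** Every block lasts 40 s. After the mother's second reply, "This will again be followed by a Count and Rest trial". Both members are then asked to "mentally (i.e., silently) reflect on the discussion while receiving neurofeedback representing the synchrony between both participants' aIC activation". There are three such runs and then a fourth: "During the transfer run, the task will be exactly the same except no neurofeedback will be presented".
- **ANALYSES, general text.** GLM coefficients "will be computed for each voxel and converted to % signal change for contrasts of interest", with Reflect versus Rest in the list. On the model: "Regressors will also include the block stimulus conditions". On methods: "All offline fMRI data preprocessing and analyses will be conducted as described elsewhere", with two citations.
- **ANALYSES, Hypothesis 2B.** The Fisher z of the 1B correlation is reused as the coupling measure.

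**The concern.** Two people who follow the same block schedule, and whose aIC rises or falls with the same block, will have correlated timecourses even if they have never met. The 1B sentence does not guard against this. It names no unrelated-pair comparison and does not say that block responses are removed first. It also sets no value that would count as success, although its companion 1A has one.

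The Specific Aims include promoting parent-child neural synchrony, and the Innovation section says the synchrony feedback is there to increase it. A correlation that strangers on the same schedule could also show would not support that. The result is meant to underpin later studies. In 2B, an association with validation or emotion ratings might reflect how strongly each person responds to Reflect, not how closely the pair is coupled.

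**Working it through.** The plan gives no figure for 1B, so there is none to reproduce.

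**Inputs from the documents.** 10 dyads (Participants). 40 s blocks, three feedback runs and one transfer run, each with one Reflect block directly after Rest (task section). TR 2 s (fMRI Data Acquisition Parameters). Hence 40/2 = 20 volumes per block, 40 for Rest plus Reflect, 3 × 20 = 60 Reflect volumes per dyad under feedback, and 20 in the transfer run.

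**Assumptions, not in the documents.** Zero coupling. Double-gamma haemodynamic response. Independent AR(1) noise, coefficient 0.3 or 0.6, SD 1. Mean Reflect response b of 0.5 or 1.0 noise SD in both members, with between-person SD 0.5. Two-sided 5% t-test of the dyads' Fisher z against zero, counting positive rejections (nominal 2.5%).

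**Step 1: readings.** Elsewhere in ANALYSES a contrast is a difference of coefficients, one number per voxel, not a timecourse. The phrase could mean (A) correlating over Rest plus Reflect volumes, (B) correlating within Reflect, (C) Reflect synchrony minus Rest synchrony, or (D) correlating contrast values across dyads. D was not simulated.

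**Step 2: expected correlation.** If both members carry the same response b·R(t) plus independent unit noise, r = b²v/(b²v + 1), where v is the variance of R in the window.

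- A, v = 0.25: b = 0.5 gives 0.0625/1.0625 = 0.06; b = 1 gives 0.25/1.25 = 0.20.
- B, v = 0.117: b = 0.5 gives 0.029/1.029 = 0.03; b = 1 gives 0.117/1.117 = 0.105.

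In B the effect comes from the rise at block onset. From 10 s into Reflect, r is 0.003 at b = 1. In general b² is the product of the two members' responses, so opposite signs make r negative and no response in one member makes it zero.

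**Step 3: simulated share of studies positive, true coupling zero.**

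| Reading | b = 0.5 | b = 1.0 |
|---|---|---|
| A, Rest plus Reflect | 14-19% | 82-93% |
| B, within Reflect | 6-7% | 29-41% |
| C, no Count response | 4-6% | 15-26% |
| C, Count half of Reflect | 4% | 11-14% |
| C, Count equal to Reflect | 2-3% | 2-3% |

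Ranges cover both noise settings and simulation error. C depends on Count because the Rest block opens with the decay of the Count response. With Count twice Reflect, the mean difference is negative (-0.06 and -0.18 to -0.20). With a zero average response, mean z is 0.00 and 2-3% are positive. With opposite responses, mean z under A is -0.06 and -0.19 to -0.20. With between-person SD 1.0, A falls to 6-7% and 33-35%, and B to 4-5% and 20-22%.

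**Step 4: does re-pairing help?** Ten mothers and ten daughters give 10 × 10 - 10 = 90 mismatched pairings. With b = 1, zero coupling and no between-person variation, mean z in real and re-paired dyads is 0.213 and 0.214 (A), and 0.114 and 0.114 (B). A one-sided 5% permutation test rejects in about 4-7% of studies. Adding a true noise correlation of 0.2 gives 0.389 against 0.215 (A) and 0.309 against 0.116 (B), with rejection in at least 99%.

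Re-pairing alone can fail if mother and daughter response sizes are related. At an assumed within-dyad correlation of 0.5, the 97.5th-percentile criterion is met in 7-9% (A) and 4% (B); with GLM residuals it is met in 2%.

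**Step 5: limits of the remedy.** If the shared feedback bar alone drove 5 / 10 / 20% of residual variance in each member, the criterion would be met in 12-17% / 36-52% / 91-99% of studies. The transfer run avoids the bar but is imprecise: the 95% half-width of mean z is 0.18-0.23, against 0.10-0.13 in the feedback runs.

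**Step 6: carry-over to 2B.** At b = 0.5 and 1.0 the dyad's z correlates with the product of the members' response sizes at 0.55-0.64 and 0.65-0.75 (A), and at 0.25-0.28 and 0.35-0.39 (B).

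**The case against.** - **Unknown response.** A reader might infer that the shared schedule alone makes 1B positive. The documents do not support that: they give neither the size nor the direction of the aIC response to Reflect. This stands, and the point is conditional for that reason. The test in the working is also assumed, since the plan names none.
- **Feasibility target.** 1B does not claim synchrony above that of unrelated pairs. Shared activation during Reflect could satisfy its wording, and a descriptive correlation in ten dyads is defensible if its limits are stated. This stands in part: whether block-adjusted synchrony is the main measure is the sponsor's choice. It does not remove the need for a reference value, given what the feedback is meant to achieve.
- **Rest as comparator.** The phrase names Rest, and Reflect minus Rest has a within-dyad reference. That reading is indeed less exposed, but only a Count response about as large as the Reflect response cancels the bias.
- **Outside sources.** A reader might infer that unadjusted timecourses will be used. The documents do not say so. Offline methods are deferred to cited work that may remove block responses and cannot be checked here. Nothing in the document says that 1B uses residuals, and the deferral does not supply a criterion or comparator within the plan.
- **2B.** A reader might infer that 2B becomes invalid. A predictor that partly measures response size does not by itself create a false association; it makes a true one harder to interpret.

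**Conclusion.** The point holds in conditional form and should be fixed before analysis. It is certain from the text that 1B has no criterion, no unrelated-pair comparison and no defined set of volumes. It is conditional that the correlation misleads: both members must respond to Reflect in the same direction and not weakly. At 0.5 noise SD the excess is small within Reflect and moderate over Rest plus Reflect. At 1.0 noise SD the latter would be positive in most studies with no coupling at all. There is no bias at a zero average response, and a negative one if the members respond in opposite directions. These sizes rest on the assumed response, noise, between-person SD and test. They do not show that the study's actual 1B result would be spurious.

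**What to change.** Under Hypothesis 1B in ANALYSES:

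1. State which volumes are correlated and how runs and dyads are combined.
2. Compare the mean Fisher z of the real dyads in the feedback runs with a permutation null from re-paired mothers and daughters (the 90 mismatched pairings). State a criterion, for example above the 97.5th percentile of that null.
3. Remove the shared block response, either with residuals from the GLM already planned or by dropping about the first 10 s of Reflect. Make this a sensitivity analysis, or the main measure if the target is synchrony beyond the shared block response. Report the unadjusted correlation alongside.
4. State that exceeding the null in the feedback runs shows synchrony beyond the shared schedule but cannot separate coupling from an effect of the bar both members see. Report the bar-free transfer run separately, as an estimate with its 95% interval.
5. In 2B, repeat the association with the adjusted z as a sensitivity analysis.

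The cost is a few sentences and a short script on data and regressors already planned. Reported synchrony may look smaller, adjusted values discard shared Reflect-level activation, and the transfer-run interval will be wide.

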**Aim 2. To determine preliminary effects of neurofeedback on neural activation and emotional experience during the dyadic social interaction. Hypothesis 2A.** Mothers' own aIC activation while listening to their daughters will be positively correlated with that of their daughters' during the mothers' response. **Hypothesis 2B.** Stronger temporal synchrony and coupling between mothers' and daughters' aIC activation during the reflection condition will be associated with more validating statements made by the mother during the task and lower self-report ratings of negative emotions in both participants.

**Aim 3. To identify short-term effects of neurofeedback training. Hypothesis 3A (Exploratory).** Mothers' and daughters' neural activation of resting-state networks will be more temporally synchronous at the end of the hyperscanning session (following neurofeedback), as compared to their first resting-state fMRI scans in the hyperscanning session. **Hypothesis 3B.** Ratings of positive emotions will be higher and negative emotions will be lower following the hyperscanning session as compared to ratings taken before the scan.

[figure not shown]
The expected outcome of the proposed study is a rt-fMRI neurofeedback-hyperscanning protocol that will be available for implementation in future studies with larger samples in order to study its effects on adolescent depression. The protocol and data from the first five dyads will be used for a K award submission in the fall of 2019. A manuscript will be prepared and submitted following the end of data collection in the summer of 2020. The protocol developed in this study will provide the foundation for future prevention and intervention efforts aimed at the effects of parenting on the development of emotion regulation skills and depressive symptoms.

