Parents will complete a phone screen to determine initial eligibility (see Inclusion/Exclusion criteria in **Table 2**). If initial study criteria are met, a 2-hour in-person lab visit will be scheduled where mothers and daughters will complete consent/assent; diagnostic interviews (the Mini-International Neuropsychiatric Interview [parent MINI 7.0, adolescent MINI KID 7.0]); surveys on emotion regulation, parenting practices, depression, and anxiety (Table 3); and additional screening. Survey data will be used for preliminary exploratory analyses. Based on data collected from the screening visit, participants will be invited to participate in the full study: a 4-hour visit where mothers and daughters will complete emotion ratings, mock scanner training, and fMRI tasks individually and together using hyperscanning (scan time = 16 min resting-state [2 runs], 7 min structural MRI, 40 min fMRI tasks, 10 min clinical MRI scans).

**Participants.** 10 adolescents (ages 13-17; all female) and their biological mothers, total  $N=20$ , recruited using electronic flyers distributed through local schools and from a previous lab project (Dyadic Inter-Brain Signaling study). Our sample will include ~40% from ethnic/racial minority groups.

**Consideration of biological variables.** This study will result in pilot data and a protocol for a future intervention study in depression. Scientific reasons to only include females are: (1) rates of depression are three times higher among females than males; (2) during adolescence, female and male brains develop at

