**Hypothesis 3B.** *Ratings of positive emotions will be higher following the hyperscanning session as compared to ratings taken before the scan.* Paired t-tests will be conducted separately for mothers and daughters to determine if ratings of positive emotions (e.g., "happy," "calm") made on a 0-10 Likert scale before the scan differ significantly from those made after the scan.

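### Hypothesis 2B relates coupling to negative emotion by a raw correlation, so mood brought to the scan could produce or mask the association; planned pre-scan ratings could be used to adjust

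*Combined protocol and SAP*

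**What the plan says.** In the ANALYSES section, Hypothesis 2B defines the exposure with one value per dyad: "Coupling will be measured as the correlation between timecourses for aIC activation as described in Hypothesis 1B, transformed to z-scores". The outcome is a self-report: each participant is asked to "rate the intensity of various emotions they felt during the scan", on a 0-10 Likert scale. The analysis is a correlation of the z-scores with the count of validating statements "and 2) ratings of negative emotions (b"). No covariate, change score or partial correlation is named, and no alpha, effect size or power is given.

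A pre-scan negative rating appears elsewhere. Under Aim 3 in Specific Aims, Hypothesis 3B predicts that "negative emotions will be lower following the hyperscanning session as compared to ratings taken before the scan". The ANALYSES text for Hypothesis 3B is narrower. It compares only positive-emotion ratings, "made on a 0-10 Likert scale before the scan differ significantly from those made after the scan". The description of the scan visit under APPROACH mentions emotion ratings without saying which emotions.

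The sample is "10 adolescents (ages 13-17; all female) and their biological mothers", so each correlation rests on 10 pairs of values. Aim 2 is framed as "To determine preliminary effects of neurofeedback on neural activation and emotional experience during the dyadic social interaction".

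**The concern.** Coupling is measured, not assigned, and there is no comparison group. A participant who arrives in low mood may report more negative emotion during the scan, and the same mood may also go with weaker or stronger coupling. The raw correlation cannot separate that from an association that arises during the task.

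The protocol's own rationale makes such a link plausible, though it does not prove it. The SIGNIFICANCE section reports right anterior insula hyperactivation in depressed adolescents and ties parent-child resting-state synchrony to daily emotional synchrony. The region of interest in ANALYSES is right-sided. The participants here, however, are psychiatrically healthy.

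The protocol and the data from the first five dyads are meant to support a career-award application, and the pilot as a whole is meant to lead to larger studies. A correlation that reflects arrival mood could be carried forward as a sign that coupling matters.

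**Working it through.** **Inputs.** From the documents: n = 10 dyads; raw Pearson correlation; no covariate. Not in the documents, hence assumed: alpha 0.05 two-sided; jointly normal variables; the correlation c of pre-scan mood with coupling; the correlation ρ of pre-scan with during-scan rating; and the size of any direct association. The plan has no figure of its own to reproduce.

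**1. Cost of the covariate.** The critical value is |r| = t/√(df + t²).
- Raw, df = 10 − 2 = 8, t = 2.306: 2.306/√(8 + 5.318) = 0.632.
- Adjusted, df = 10 − 3 = 7, t = 2.365: 2.365/√(7 + 5.591) = 0.666.

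**2. Confounding.** If coupling and during-scan emotion are linked only through pre-scan mood, the raw correlation is c × ρ. Rejection rates come from 200,000 simulated trials of 10 dyads per row.

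| c | ρ | raw r = c × ρ | raw test rejects | adjusted test rejects |
|---|---|---|---|---|
| −0.3 | 0.3 | −0.09 | 0.057 | 0.05 |
| −0.5 | 0.5 | −0.25 | 0.106 | 0.05 |
| −0.5 | 0.7 | −0.35 | 0.168 | 0.05 |
| −0.7 | 0.7 | −0.49 | 0.312 | 0.05 |

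**3. Masking.** The raw correlation is cρ + p√((1 − c²)(1 − ρ²)), where p is the partial correlation. With p = −0.6 and mood related positively to coupling (c = ρ = 0.5), it is 0.25 − 0.6 × 0.75 = −0.20. A sizeable association would look weak.

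**4. Power when mood is unrelated to coupling (c = 0).** Hold the partial correlation at −0.6. The raw correlation is then −0.6√(1 − ρ²).

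| ρ | raw r | power, raw | power, adjusted |
|---|---|---|---|
| 0 | −0.60 | 0.48 | 0.43 |
| 0.3 | −0.57 | 0.44 | 0.43 |
| 0.5 | −0.52 | 0.35 | 0.43 |
| 0.7 | −0.43 | 0.24 | 0.43 |

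Holding the raw correlation at −0.5 instead gives the same pattern. Raw power is about 0.33; adjusted power is 0.29 at ρ = 0, 0.32 at 0.3, 0.35 at 0.4 and 0.62 at 0.7. Break-even lies at ρ of about 0.3 to 0.4.

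**5. Power when mood does confound.** Take a raw correlation of −0.5 with c = −0.5 and ρ = 0.5. The partial correlation is (−0.5 + 0.25)/√(0.75 × 0.75) = −0.33. Power falls from 0.33 raw to 0.14 adjusted, because the part due to mood has been taken out.

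**6. Precision.** By the Fisher approximation, 80% power needs |r| of about 0.79 raw and 0.82 adjusted. The 95% interval on the z scale has half-width 1.96/√7 = 0.74 raw and 1.96/√6 = 0.80 adjusted. Both are wide.

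**The case against.** The strongest reply has four parts.

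- **Power.** A reader might infer that the raw analysis simply wastes power. The documents do not support that, because they give no pre/during correlation and adjustment costs power when it is low. A low value is plausible: the outcome is emotion felt while discussing situations chosen for strong negative feeling, and participants have no current psychiatric diagnosis, so pre-scan negative ratings may cluster near zero. This stands. The power gain and the confounding are also separate scenarios, as steps 4 and 5 show.
- **Error rate.** A reader might take the upper rejection rates as Type I error of Hypothesis 2B as written. They are not. The hypothesis asserts an association, and under those scenarios a marginal association exists. They are false positives only if the result is read as coupling mattering beyond arrival mood. They also need strong assumed correlations; at 0.3 and 0.3 the raw rate is about 6%. This stands, but the wording of Aim 2 speaks of effects on emotional experience and so invites the stronger reading.
- **Baseline.** It is tempting to treat the pre-scan negative rating as assured. It rests on Specific Aims alone; the analysis text for Hypothesis 3B names only positive emotions. Nor is it stated whether daughters give their ratings before or after being asked to recall upsetting situations. If after, the covariate partly captures task-related emotion. This stands and belongs in the fix.
- **Proportion.** This is a 10-dyad feasibility study with preliminary aims, so the choice of correlation may look like preference. That limits the weight of the point. It does not argue against an added analysis that keeps the raw one.

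**Conclusion.** The point holds as one about confounding. As planned, Hypothesis 2B cannot distinguish mood brought to the scan from mood associated with coupling during it, although a suitable covariate appears to be planned. Under mood-coupling and pre/during correlations of 0.3/0.3 to 0.7/0.7 in size and no direct association, the raw test rejects in about 6% to 31% of trials and the adjusted test in 5%. These figures rest on assumed correlations, normal data and an assumed two-sided 0.05 test.

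Greater power is not a reason in itself. With mood unrelated to coupling and a partial correlation of 0.6 in size, adjustment ranges from a loss of about 0.05 (0.48 to 0.43) to a gain of 0.19 (0.24 to 0.43), depending on an unknown correlation. With 10 dyads power is modest either way, so the estimates and their intervals carry the information. The change is worth making because it is cheap and the raw result is kept.

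**What to change.** - In Hypothesis 2B, add for mothers and daughters separately the partial correlation (or regression) of the negative-emotion rating on Fisher-z coupling, adjusted for that person's own pre-scan negative-emotion rating. Report it with a confidence interval beside the raw correlation and its interval.
- Reconcile the two statements of Hypothesis 3B so that negative emotions are clearly rated before the scan, and state whether that rating comes before the daughter is asked to recall emotional situations.
- Word the conclusion as an association, and give confounding as the reason for adjusting.

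The cost is a line or two of wording and one of 8 degrees of freedom, with no new data if the ratings are taken as Specific Aims implies. Power drops slightly if the pre/during correlation is low, and the association will usually be smaller than the raw one if mood does confound in the hypothesised direction.

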**Table 2: Inclusion/Exclusion Criteria**

Criteria	Moms	Girls
Inclusion		
Eligible for fMRI	✓	✓
Sufficient English fluency to complete tasks	✓	✓
BMI	18.0-40.0	16.0-40.0
Right-handed	✓	✓
Biological female	✓	✓
Biological mother	✓	
Co-residing at least 4 days/week	✓	✓
Primary caregiver > 50% of child's lifespan	✓	
Age 13-17		✓
Exclusion		
Current psychiatric diagnosis	x	x
Medications influencing fMRI	x	x
Medical conditions influencing fMRI	x	x
Alcohol or psychoactive drug on scan day	x	x
Neurodevelopmental delay		x
History of mood or psychotic disorder		x
History of OCD or ADHD		x

different rates, with some studies indicating a gap in brain maturation due to the onset of puberty occurring two years earlier for girls; (3) many adolescents do not have a consistent father figure in the home, with rates of 1 in 4 children living in single mother families; and (4) mothers and fathers diverge in emotion socialization techniques and parenting styles that could impact results.

**fMRI hyperscanning.** All hyperscanning experiments will be conducted on two MR750 3T MRI scanners with fMRI imaging protocols and parameters described elsewhere. Prior to scanning, participants will complete a brief training session in the mock scanner to desensitize them to the MRI environment and to practice talking while remaining as still as possible. After this training, subjects will complete an 8-minute eyes-open resting-state scan followed by the dnf training and transfer runs. Subjects will then undergo a second resting-state scan and complete post-scan emotion rating scales.

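### Hypothesis 3A predicts temporal synchrony but its statistic measures similarity of connectivity pattern, and the negative-emotion half of Hypothesis 3B has no analysis

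*Combined protocol and SAP*

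**What the plan says.** **3A (exploratory).** Specific Aims, Aim 3, predicts that "neural activation of resting-state networks will be more temporally synchronous at the end of the hyperscanning session", compared with the first resting-state scans. ANALYSES, Hypothesis 3A, repeats the prediction. It calls the measure similarity of resting-state networks and then builds it in two steps:

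- within each person: "On the individual level, a matrix of correlation coefficients for all possible pairs of resting-state networks will be created" and Fisher-transformed;
- within each dyad: the matrices are "then vectorized and correlated between each pair of mother-daughter dyads to determine the level of synchrony within the dyad".

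A paired t-test then compares the beginning with the end of the session.

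Hypothesis 1B also concerns temporal synchrony, of the anterior insula (aIC), and measures it differently: "Correlations will be calculated between mothers' and daughters' aIC timecourses". Hypothesis 2B Fisher-transforms that correlation and calls it coupling.

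**3B.** Specific Aims, Aim 3: "Ratings of positive emotions will be higher and negative emotions will be lower following the hyperscanning session". ANALYSES, Hypothesis 3B: "Ratings of positive emotions will be higher following the hyperscanning session as compared to ratings taken before the scan". Paired t-tests follow for positive ratings, separately for mothers and daughters. The only other planned analysis of negative ratings is in 2B, where "Participants will be asked to rate the intensity of various emotions they felt during the scan" and those ratings are correlated with coupling.

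**The concern.** In 3A one word, synchrony, covers two different quantities. Two people can have very similar connectivity patterns without their signals rising and falling together, and the reverse also holds. A significant paired t-test would be reported as increased synchrony although it can arise with no mother-daughter coupling. A real rise in coupling would mostly be missed.

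In 3B the negative half of the prediction disappears between the aims and the analysis section. Daughters are asked to talk in the scanner about recent situations of intense negative emotion, so whether negative emotion fell or rose afterwards is a basic result. Nothing in the analysis section commits the study to reporting it, and 3B could be called supported on positive items alone.

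**Working it through.** The documents give no alpha, sidedness, effect size or power for 3A or 3B, so there is no stated figure to reproduce.

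**3A: algebra.** Let x_i(t) and x_j(t) be the signals of networks i and j in one person.

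- Matrix entry: z_ij = atanh(corr over t of x_i(t), x_j(t)).
- Planned statistic: S = corr(vec z of mother, vec z of daughter).

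Reordering the daughter's time points changes none of her z_ij, because both of her signals are reordered together. S is therefore unchanged, whatever the number of networks or the strength of coupling. In 1,000 simulated dyads per scenario, random reordering changed S by less than 1e-15.

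**3A: simulation.** Inputs from the documents: 8-minute rest scan (fMRI hyperscanning) and TR 2 s (fMRI Data Acquisition Parameters), so 480 / 2 = 240 volumes; 10 dyads (Participants). Assumed: 10 networks (10 × 9 / 2 = 45 pairs), AR(1) autocorrelation of 0, 0.5 or 0.8, low or high between-person differences in connectivity, and 300 simulated studies per setting. A result counts as significant at two-sided 0.05 only if the change is upward, so the nominal false-positive rate is 2.5%.

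*Time shift of one member (circular):*

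| Shift | S | Mean timecourse r |
|---|---|---|
| none | 0.585 | 0.431 |
| 10 s | 0.585 | -0.008 |
| 30 s | 0.585 | 0.004 |
| 120 s | 0.585 | 0.030 |

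*Coupling rises, connectivity patterns fixed* (shared fraction 0 to 0.5; mean timecourse r from 0 to 0.40-0.48), six settings:

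| S before → after | Change | Planned test significant | Timecourse test significant |
|---|---|---|---|
| 0.791 → 0.802 | 0.011 | 8% | 100% |
| 0.411 → 0.417 | 0.006 | 5% | 100% |
| 0.765 → 0.780 | 0.015 | 11% | 100% |
| 0.405 → 0.415 | 0.010 | 5% | 100% |
| 0.686 → 0.722 | 0.036 | 15% | 100% |
| 0.362 → 0.387 | 0.025 | 8% | 100% |

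*No coupling, connectivity patterns converge* (person-specific deviation 0.7 to 0.5), three settings:

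| S before → after | Planned test significant | Timecourse test significant |
|---|---|---|
| 0.415 → 0.595 | 100% | 3% |
| 0.394 → 0.568 | 100% | 4% |
| 0.351 → 0.508 | 92% | 3% |

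**3B: aims against analyses.**

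| Post versus pre | Mothers | Daughters |
|---|---|---|
| Positive ratings | paired t-test | paired t-test |
| Negative ratings | none | none |

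With one composite per valence, 2 of the 4 predicted contrasts have no test. The 2B analysis does not fill the gap: it relates emotions felt during the scan to coupling and has no before-scan comparator.

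**Cost of adding the two tests.** At an assumed two-sided 0.05 with independent tests, the chance of at least one false positive is 1 - 0.95^2 = 9.8% for two tests and 1 - 0.95^4 = 18.5% for four. For a paired t-test with n = 10 (9 degrees of freedom, noncentrality d × √10), power is 29% at d = 0.5 and 62% at d = 0.8, and reaches 80% at d of about 1.0.

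**The case against.** **On 3A:** it is labelled exploratory, its method section opens with the word similarity, and every step is specified. The background sections already use synchrony when citing the study whose method 3A adopts, so the ill-fitting word is mainly *temporally*. The statistic itself is valid. The 1B measure concerns one region during a feedback task, and the plan never says that timecourse coupling is what it wants at rest. The simulated percentages also depend on chosen settings, and 100% is a strong-coupling case. In further runs with autocorrelation 0.8, the timecourse test was significant in 39% of studies at a mean r of about 0.04 and in 76% at about 0.08, reaching 100% from about 0.16.

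**On 3B:** Aim 3 states both the prediction and its comparator, so what is missing is a named test. Dropping the prediction from the aim would also restore consistency. The test counts assume one composite per valence, which the plan does not specify, and independence is doubtful for ratings from the same people.

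**What stands:** the percentages illustrate direction and are not forecasts for this study. In those further runs the planned test stayed at 1-7%, so the direction held. The algebraic result needs none of these settings. The exploratory label lowers the weight of 3A but does not make its stated conclusion follow from its test. 3B carries no exploratory label. Neither point affects the Aim 1 feasibility analyses.

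**Conclusion.** Both halves hold, as points that should be corrected.

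- **3A:** the planned paired t-test can support a statement about connectivity similarity but not about temporal synchrony. This is exact and assumption-free. The size of the mismatch (5-15% detection of a large rise in coupling; 92-100% significance with no coupling) rests on the assumed networks, autocorrelation, between-person differences and coupling levels.
- **3B:** an aims-versus-analysis inconsistency that leaves negative emotion in mothers and in daughters without a pre/post test. The count of 2 of 4 assumes one composite per valence.

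**What to change.** **3A, one of two options:**

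1. In Aim 3 and in ANALYSES, restate the hypothesis as greater similarity of resting-state connectivity pattern at the end of the session, and call the outcome similarity throughout. This costs wording only.
2. To keep the temporal claim, add the mother-daughter correlation of matched network timecourses (Fisher z, as in 2B) for the first and last rest runs, compared by the same paired t-test. This requires the two scanners' rest runs to be acquired simultaneously. The protocol places them in the hyperscanning session but does not say so outright, and it should.

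**3B:** restore the negative clause in ANALYSES and add paired t-tests of pre- versus post-scan negative ratings, separately for mothers and daughters. Pre-specify one mean composite per valence. The schedule already provides for post-scan ratings ("Subjects will then undergo a second resting-state scan and complete post-scan emotion rating scales"), but confirm that the negative items are on both the pre- and post-scan forms. Report mean change with 95% confidence intervals for both valences, so that 3B is not called fully supported on positive items alone. No rule that both must be significant is needed. Deleting the negative prediction from Aim 3 would also be consistent, but it gives up a result the planned ratings could supply.

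**Cost:** no new visits or scans. Acknowledge the rise in the chance of any false positive from 9.8% to 18.5% under the assumptions above. With 10 pairs, estimates and intervals should carry more weight than significance verdicts.
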